13      Institutional research policies and procedures.

14        **1.1 Specific Aims and Hypothesis**

15        The primary aim of this study is to compare the 30 and 90-day overall/cumulative grade III or  
16        higher complication rates between patients with severe obstructive jaundice undergoing  
17        preoperative endoscopic biliary drainage with SEMS and patients undergoing direct surgical  
18        resection. In this study, **One arm undergoes preoperative biliary drainage followed by surgery and**  
19        **the other arm undergoes surgical resection** without prior biliary drainage. Secondary aims will be  
20        to compare surgical outcomes including mortality, intra-operative parameters, hospital length of  
21        stay, ICU length of stay, readmission rate and time to commencement of adjuvant treatment.

22        **1.2 Background and Rationale**

23        Despite the fact that endoscopic and percutaneous placement of biliary stents is technically  
24        successful in 90-95% of cases, routine preoperative biliary drainage for pancreatic cancer remains  
25        controversial.[4, 5] Pooled data from retrospective studies published over the past several years  
26        have shown similar rates of 30-day mortality after pancreaticoduodenectomy in those who have  
27        undergone biliary decompression as compared to those who have not. A few studies have  
28        suggested that routine preoperative drainage in patients undergoing surgery for cancer of the  
29        pancreatic head may increase overall complications, likely due to complication related to the  
30        endoscopy itself (i.e. pancreatitis, bleeding, perforation) and complications related to stent  
31        failure.[6] In the largest, multicenter, randomized trial to date, patients were randomly assigned  
32        to undergo either endoscopic preoperative biliary drainage for 4 to 6 weeks, followed by surgery,  
33        or surgery alone after diagnosis. In this study, endoscopic preoperative biliary drainage did not  
34        have a beneficial effect on the surgical outcome but rather was associated with an increase in  
35        serious complications.[7]

36  
37        On the other hand, outcome measures have not been standardized and the lack of complete data  
38        on surgical complications following preoperative drainage make direct comparisons difficult and  

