65 obstruction prior to surgery. This represents the first biliary metal stent with labeling to support  
66 pre-operative drainage in the US.

67 **1.4 Preclinical Data**

68 Please see clinical data below

69 **1.5 Clinical Data to Date**

70 A recent meta-analysis of 1989 patients showed that SEMS have higher stent insertion success,  
71 lower risk of stent occlusion, lower re-intervention rate, fewer therapeutic failures, and fewer  
72 episodes of cholangitis compared to plastic stents making them the optimal choice for biliary  
73 decompression.[8] Also a recent randomized controlled trial confirmed that SEMS are superior to  
74 plastic stents with regard to functional stent time and showed that the total health care cost is  
75 similar for placing SEMS or plastic stents even in patients with survival less than 3 months

76 **1.6 Dose Rationale and Risk/Benefits**

77 The study doesn't involve drug administration.

78 **2.0 STUDY OBJECTIVES**

79 **2.1 Primary Objective:**

80 The primary aim of this study is to compare the 30 and 90-day overall complication rates between  
81 patients with severe obstructive jaundice undergoing preoperative endoscopic biliary drainage  
82 with SEMS and patients undergoing direct surgical resection.

83 **2.2 Secondary Objective:**

84 Secondary aims will be to compare surgical outcomes including hospital length of stay, ICU  
85 length of stay, readmission rate, disposition from hospital, emergency room visits, urgent care  
86 center visits and time to commencement of adjuvant treatment.

87 **3.0 STUDY DESIGN**

88 **3.1 General Design**

89 This is a Randomized controlled trial.

92 ERCP will be performed on those who are randomized to the intervention group with 24 hours of  
93 randomization. The patient will be followed at 30 days and 90 days post-operatively.

94 **3.2 Primary Study Endpoints**

95 30 and 90 day- complication rates between patients with severe obstructive jaundice undergoing  
96 preoperative endoscopic biliary drainage with SEMS and patients undergoing direct surgical  
97 resection

98 **3.3 Secondary Study Endpoints**

99 Secondary aims include the total number of complications, intraoperative estimated blood loss,  
100 number of required fluid boluses, postoperative hospital LOS, readmission rate, disposition from  
101 hospital, time to commencement of adjuvant treatment, emergency room visits, urgent care center  

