102 visits, and perioperative mortality. Complications will include pancreatic fistula, delayed gastric  
103 emptying, intra-abdominal abscess, cardiac complications, respiratory complications, deep vein  
104 thrombosis, pulmonary embolism, urinary tract infection, wound infection, acute renal failure,  
105 hemorrhage, hepaticojjunostomy leak, and duodenojjunostomy leak. Pancreatic fistula was  
106 defined and graded according to the International Study Group of Pancreatic Fistula criteria.  
107 Delayed gastric emptying was defined and graded according to the International Study Group of  
108 Pancreatic Surgery. Wound infections and urinary tract infection were defined according to the  
109 Centers for Disease Control and Prevention guidelines. Cardiac complications were defined  
110 according to the American College of Cardiology and renal complications were defined by the  
111 Acute Dialysis Quality Initiative.

112 **3.4 Primary Safety Endpoints**

113 Both SEMS placement and direct surgical resection are considered acceptable standard of care  
114 practices.

115 **4.0 SUBJECT SELECTION AND WITHDRAWAL**

116 **4.1 Inclusion Criteria**

117 -Adult patients age >18 regardless of gender or ethnicity  
118 -Patients with peri-ampullary pancreatic cancer.  
119 -Patients with serum bilirubin greater than 10mg/dL  
120 -Adequate birth control

121 **4.2 Exclusion Criteria**

122 -Patients with evidence of distant metastasis on CT or MRI  
123 -Patients anticipated to require vascular reconstruction  
124 -Patients with cholangitis  
125 -Patients who previously underwent biliary decompression for cholangitis by ERCP or PTC  
126 -Patients with low performance score (Karnofsky performance status scale < 50)  
127 -Patients with known preexisting liver disease with associated elevated bilirubin  
128 -Patients who are pregnant or actively breast feeding.

129 **4.3 Gender/Minority/Pediatric Inclusion for Research**

130 Any patient can be included if older than 18 years of age irrespective of gender, color, or  
131 ethnicity.

133 4.4 Subject Recruitment and Screening

134 One Hundred patients older than 18 years with periampullary cancer presenting with jaundice and  
135 total bilirubin greater than 10mg/dL will be included in the study.

136 Patients will be recruited from clinic (gastroenterology and pancreaticobiliary surgery) or when  
137 admitted to the hospital for workup and/or management and will be consented at that time.

138

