139 4.5 Early Withdrawal of Subjects

140 **4.5.1 When and How to Withdraw Subjects**

141 Patients can withdraw from the study at any time. Stent placement is the standard of care and thus  
142 subjects who elect to withdraw from the study will continue to have the biliary stent in place and  
143 be followed regularly similar to patients that are enrolled in the study.

144 **4.5.2 Data Collection and Follow-up for Withdrawn Subjects**

145 Subjects who elect to withdraw from the study will continue to be followed on a regular basis.  
146 Data that is important to the integrity of the final study analysis and the safety profile of the  
147 SEMS will be collected after obtaining approval of the subjects.

148

149 **5.0 STUDY DRUG/THERAPY**

150 5.1 Description

151 The stents to be used in this study are FDA approved WallFlex Biliary RX Stents (Boston  
152 Scientific Corporation, Natick, MA, USA) which are available in diameters of 8 or 10 mm and  
153 lengths of 40, 60, and 80 mm.

154 5.2 Treatment Regimen

155 Stent to be placed pre-operatively in the intervention group to be removed during surgery.

156 5.3 Risks

• Pain	• Infection	• Tumor overgrowth around ends of stent
• Bleeding	• Inflammation	• Mucosal hyperplasia
• Fever	• Recurrent obstructive jaundice 26% (likely)	• Cholangitis
• Nausea	• Stent occlusion	• Cholecystitis 10% (likely)
• Vomiting	• Tumor ingrowth through the stent	• Pancreatitis 6% (possible)
• Bile duct ulceration	• Perforation of duodenum or bile duct	• Stent migration 8% (possible)
• Perforation of the gall bladder due to the stent covering the cystic duct	• Stent misplacement	

157

158

159 Once again, placement of SEMS is the standard of care for patient with profound jaundice despite  
160 the lack of evidence to support this practice.

161 5.4 Method for Assigning Subjects to Treatment Groups  
162 A randomization schedule will be created by the study statistician using the method of random  
163 permuted blocks. Randomization assignments will be loaded into a REDCap database before  
164 study enrollment begins. Randomization assignments will be accessed through the REDCap  
165 randomization facility.

166 5.5 Preparation and Administration of Study Drug/Therapy  
167 The intervention group will receive a WallFlex Biliary RX Stents (Boston Scientific Corporation,  
168 Natick, MA, USA)

169 5.6 Subject Compliance Monitoring  

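### The only list of complications (3.3) does not name most of the ERCP, stent and biliary harms the protocol itself expects, and nothing else defines what the primary rate counts

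*Combined protocol and SAP*

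**What the plan says.** Section 1.1 sets a broad target: "The primary aim of this study is to compare the 30 and 90-day overall/cumulative grade III or" higher complication rates, drainage followed by surgery against surgery alone. Section 3.2 repeats the 30- and 90-day rates without saying what a complication is. Section 7.2 compares grade III or higher rates as a risk difference, stent minus control, and also adds no definition.

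The only list is in 3.3, Secondary Study Endpoints. That section opens "Secondary aims include the total number of complications, intraoperative estimated blood loss" and a few lines later introduces the list with "Complications will include pancreatic fistula, delayed gastric". It continues "emptying, intra-abdominal abscess, cardiac complications, respiratory complications, deep vein" thrombosis, then names pulmonary embolism, urinary and wound infection and renal failure, and closes with "hemorrhage, hepaticojjunostomy leak, and duodenojjunostomy leak. Pancreatic fistula was" (the last words begin the next sentence).

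Two other sections describe the harms of drainage. Section 1.2 reports that routine drainage before surgery for cancer of the "pancreatic head may increase overall complications, likely due to complication related to the" endoscopic procedure, with pancreatitis, bleeding and perforation as examples, and to stent failure. Section 5.3 lists the stent risks and gives rates for four: "Recurrent obstructive jaundice 26% (likely"), "Cholecystitis 10% (likely"), stent migration 8% and pancreatitis 6%. It also lists cholangitis, stent occlusion, and perforation of the duodenum, bile duct or gallbladder, without rates.

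On timing, the Study Summary and 3.1 place follow-up at 30 and 90 days after the operation. Section 8.1 collects adverse events from randomization to 90 days after surgery. Section 5.8 says the study is unblinded, and 6.1 takes primary endpoint data from the electronic record.

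**The concern.** The trial compares two strategies, and one of them adds a procedure and a device before the operation. A fair overall comparison has to count the harms of that added step alongside any surgical harm it prevents. The only list is nearly all on the surgical side of that balance.

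The omission is not even between arms. ERCP and stent events occur mainly in the stent arm, so a count built on the list would lower the stent-arm rate more than the control rate. The risk difference in 7.2 and the secondary total of complications would both move towards stenting. Cholangitis in an undrained control patient waiting for surgery is also unlisted, which pulls the other way.

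With no definition in 3.2 or 7.2, whether a given biliary event counts is left to whoever reads the record, and that person may know the assigned arm.

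**Working it through.** **Passages side by side**

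| Harm expected in 5.3 | Rate in 5.3 | Named in 3.3? |
|---|---|---|
| Recurrent obstructive jaundice | 26% | No |
| Cholecystitis | 10% | No |
| Stent migration | 8% | No |
| Pancreatitis | 6% | No |
| Cholangitis | none | No |
| Stent occlusion | none | No |
| Perforation (duodenum, bile duct, gallbladder) | none | No |
| Bleeding | none | Hemorrhage is listed with no cause, so possibly |
| Infection | none | Partly (wound, urinary, abscess) |

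All four harms that have a rate are absent from the list. Of the three endoscopic harms named in 1.2, two (pancreatitis and perforation) are absent.

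**The plan's own figure.** Inputs from 7.1: 50 per arm, control rate 50%, one-sided 0.05. With p_c and p_s the control and stent rates and p̄ their mean:

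Power = Φ[(p_c − p_s − 1.645·√(2p̄(1−p̄)/50)) / √((p_c(1−p_c) + p_s(1−p_s))/50)]

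For p_s = 25, 30 and 35% this gives 83.4, 65.7 and 44.9%. The plan states 84, 66 and 44%, so the formula reproduces it to within about one point and there is no arithmetic error.

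**Illustration 1: no true net benefit.** Let q be the share of stent patients with an uncounted grade III or higher event. The documents give no value for q, so it is assumed, over 5 to 20%. Such events are taken as independent of the counted ones. Both true all-in rates are set to 50%, and controls are first given no uncounted events.

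Counted stent rate = 1 − 0.5/(1 − q).

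For q = 10%: 1 − 0.5/0.9 = 44.4%, so the apparent difference is 5.6 points. The two standard errors are √(2 × 0.472 × 0.528/50) = 0.0998 and √((0.250 + 0.247)/50) = 0.0997. The chance of declaring success is Φ[(0.0556 − 1.645 × 0.0998)/0.0997] = Φ(−1.09) = 13.8%.

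The last column repeats this with half as many uncounted events in controls, so that the counted control rate is 1 − 0.5/(1 − q/2).

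| q | Counted stent rate | Chance of declaring stenting effective, controls none | Same, controls q/2 |
|---|---|---|---|
| 5% | 47.4% | 8% | 7% |
| 10% | 44.4% | 14% | 9% |
| 15% | 41.2% | 22% | 12% |
| 20% | 37.5% | 35% | 17% |

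The nominal value is 5%. All figures are for one time point. Section 7.2 requires success at both 30 and 90 days, which can only lower them.

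**Illustration 2: a real surgical benefit.** Take a counted stent rate of 30% against a control rate of 50%. The all-in stent rate is 1 − 0.7(1 − q), which is 33.5, 37.0, 40.5 and 44.0% for the four values of q. The difference shrinks from −20 points to −16.5, −13.0, −9.5 and −6.0. Power with everything counted is 51, 37, 24 and 15%, against 66% when these events are left out.

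**The case against.** The strongest reply is that the list was never meant to define the primary endpoint. It sits under secondary endpoints, next to the total number of complications, and its verb is open-ended. The primary outcome is set by severity in 1.1, 7.1 and 7.2, so on a plain reading a grade III perforation or cholangitis already counts. No section tells an abstractor to work from the list, and the case report form is not in the available text. Drainage harms are in any case recorded as adverse events from randomization.

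Most of this stands as a limit on the claim. A reader might infer that the plan excludes every ERCP and stent event, or that the primary comparison certainly leaves out the main harms of stenting. The documents support neither. Hemorrhage is listed without a cause and may cover bleeding after ERCP, listed infections overlap the infection risk in 5.3, and nothing says the list is exhaustive or governs the primary rate.

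The reply does not remove the gap. Neither 3.2 nor 7.2 supplies another definition. Recording an event as an adverse event does not put it into the 7.2 risk difference, and the form in 8.2 grades events as mild, moderate or severe, not as grade III or higher. The total count is directly affected, because the list follows from it.

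A second objection is also sound: the list cannot be repaired without the clock. The stent is removed at surgery (5.2), so occlusion, migration and obstruction through it arise mainly before the operation. With follow-up dated from surgery, a longer list alone would still miss most of them.

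A third concerns size. It is tempting to multiply 50 stented patients by the 5.3 rates and announce 13 recurrent obstructions and 5 cases of cholecystitis. Those rates carry no grade and no time horizon, and the categories can overlap. They cannot serve as expected grade III or higher counts.

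**Conclusion.** The point holds as an undefined endpoint with a one-sided list. It is not a stated exclusion. The protocol's only list leaves out most of the biliary, ERCP and stent harms it expects, and the sections that define and analyse the primary rate do not fill the gap. If the list is used for counting, the bias runs towards stenting as long as uncounted events are more frequent in the stent arm.

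The size is illustrative. The 8 to 35% range rests on an assumed q of 5 to 20%, independence, no uncounted control events, true all-in rates of 50% in both arms, and a single time point. Giving controls half as many uncounted events cuts it to 7 to 17%. The documents do not show where in these ranges the trial would fall. The change should be made before outcome data are abstracted.

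**What to change.** In 3.2, 3.3 and 7.2:

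- State that any grade III or higher complication counts in both arms, whether or not it is listed.
- Count from randomization to 30 and 90 days after surgery. The start and the 90-day end then match the adverse event period in 8.1.
- Add to the list, for both arms: cholangitis; cholecystitis; pancreatitis after ERCP; ERCP-related bleeding (or say that hemorrhage covers it); perforation of duodenum, bile duct or gallbladder; stent occlusion or migration; and recurrent or persistent biliary obstruction needing unplanned intervention.
- Report post-operative surgical complications and biliary or procedural complications separately, as supportive results.

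The cost is protocol wording and a few rows on the case report form, since these events already fall under adverse event collection. The downside is that the counted stent-arm rate may rise, so the result may look less favourable to stenting and power may fall, as the second illustration shows.

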## **List of Abbreviations**

SEMS; Self Expanding Metal Stents

ERCP; Endoscopic Retrograde Cholangiopancreatogram

CBC; Complete Blood Count

CMP; Comprehensive Metabolic Panel

INR; International Normalized Ratio

1 Study Summary

Title	Preoperative Endoscopic Biliary Drainage with Self Expanding Metal Stents (SEMS) vs. Direct Surgical Resection for Patients with Severe Obstructive Jaundice
Short Title	Pre-surgery biliary stent placement vs. direct surgery in patient with obstructive jaundice
Protocol Number	
Phase	N/A
Methodology/Study Design	Randomized control trial
Study Duration	24 months
Study Center(s)	Thomas Jefferson University
Objectives	Investigate the advantage of using biliary SEMS in patients with severe jaundice prior to surgical resection
Number of Subjects	100
Diagnosis and Main Inclusion Criteria	Patients with periampullary cancer with profound jaundice
Study Therapy, Dose, Route, Regimen	Pre-operative SEMS placement vs direct surgical resection
Duration of administration and follow-up	Patient outcome data will be monitored at 30 days and 90 days post resection surgery.
Reference therapy	Direct surgery without stent placement
Statistical Methodology	This is a superiority trial of early surgery without biliary stenting, as compared with preoperative biliary drainage in patients with severe obstructive jaundice
Schema	<pre> graph LR     A[100 patients] --> B[50 patients with preoperative stent placement]     A --> C[50 patients without preoperative stent placement]     B --> D[Grade III or higher complication]     B --> E[No complications]     C --> F[Grade III or higher complication]     C --> G[No complications]   </pre>

3        **1.0 INTRODUCTION**

4        Pancreatic cancer is the second most common digestive cancer and fourth leading cause of cancer  
5        death in the United States for both men and women. Pancreatic tumors arising in the peri-  
6        ampullary region present with biliary obstruction in 64-77% of cases. Preoperative biliary  
7        decompression has been advocated in an attempt to reduce postoperative complications following  
8        attempted curative-intent surgery.

9  
10      This document is a protocol for a human research study. This study is to be conducted according  
11      to US and international standards of Good Clinical Practice (FDA Title 21 part 312 and  
12      International Conference on Harmonization guidelines), applicable government regulations and  

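### Section 4.2 excludes earlier biliary drainage only when it was done for cholangitis, so a patient drained for another reason could be randomised to a control arm defined as undrained

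*Combined protocol and SAP*

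**What the plan says.** **Control arm.** Section 1.1 contrasts drainage followed by surgery with surgical resection "without prior biliary drainage". The Study Summary names the reference therapy as "Direct surgery without stent placement".

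**Eligibility.** Section 4.1 requires peri-ampullary cancer and admits "Patients with serum bilirubin greater than 10mg/dL". Section 4.2 has two entries that concern cholangitis. One is "Patients with cholangitis". The other is "Patients who previously underwent biliary decompression for cholangitis by ERCP or PTC". No other inclusion or exclusion criterion mentions earlier drainage or an existing stent.

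**Screening and analysis.** Section 6.1 asks for the inclusion criteria, the cancer diagnosis and basic blood tests. Section 7.3 analyses everyone as randomised and adds a per-protocol analysis if any patient does not receive the assigned surgical technique.

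**The concern.** Active cholangitis is already a separate exclusion, so the reference to cholangitis in the second entry does real work: it limits the bar on earlier drainage to one indication. Drainage for any other reason is left open.

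The protocol's own text makes such patients plausible. Section 5.3 says that "placement of SEMS is the standard of care for patient with profound jaundice", which is the target population. Section 1.2 gives pruritus and coagulation disturbance as reasons to drain. Section 4.4 recruits from gastroenterology and surgical clinics and from inpatients under work-up or management, where a stent may already have been placed.

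The trial compares drainage with no drainage. A control who arrives with a stent has already had the exposure under test and cannot receive the condition that defines the arm. A previously drained patient in the stent arm may have had another stent type or may need a second ERCP. Both blur what the risk difference in Section 7.2 estimates, and the planned power leaves little to spare.

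**Working it through.** **1. Can such a patient pass the written criteria?** Take a patient with peri-ampullary cancer, drained earlier for jaundice, without cholangitis and otherwise eligible.

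- Section 4.2, cholangitis: not met, so not excluded.
- Section 4.2, earlier decompression: the reason was not cholangitis, so not excluded.
- Section 4.1, bilirubin above 10 mg/dL: a well-working stent would usually bring the value down and keep the patient out. The criterion sets no timing relative to earlier drainage, so a recent, occluded or failed stent can still pass. Section 5.3 lists stent occlusion, stent migration at 8% and recurrent obstructive jaundice at 26%.
- Section 6.1: no check for an existing stent is described.
- Section 7.3: a pre-stented control who has the planned resection has received the assigned surgical technique, so the per-protocol analysis would not clearly pick the patient out.

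The patient can be enrolled and can be assigned to control.

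**2. The plan's own power.** Inputs from Section 7.1: 50 per arm, control rate 50%, one-sided 0.05 (z = 1.645), true stent-arm rates of 25%, 30% and 35%; stated power 84%, 66% and 44%.

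Normal approximation with pooled null variance, at 25%: mean rate (0.50 + 0.25)/2 = 0.375; null standard error √(2 × 0.375 × 0.625/50) = 0.0968; alternative standard error √(0.50 × 0.50/50 + 0.25 × 0.75/50) = 0.0935. Power = Φ[(0.25 − 1.645 × 0.0968)/0.0935] = Φ(0.97) = 83.4%. The same formula gives 65.7% at 30% and 44.9% at 35%. The stated figures reproduce to within one point, and they assume a fully undrained control arm.

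**3. Power if some controls are already drained.** Let f be the fraction of controls already drained. The documents give no value for f; 5%, 10% and 20% are assumptions, equal to 2.5, 5 and 10 of 50 controls. The risk these controls carry is also unknown, so two cases are shown. Power is the exact binomial probability that the upper one-sided 95% limit for stent minus control, with unpooled variance, lies below 0 at a single time point. With f = 0 this gives 84.7% at a true 25% and 67.1% at a true 30%, about one point above the protocol's 84% and 66% because the variance is unpooled.

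- *Case A:* drained controls keep the 50% risk and the stent arm is unchanged. The control rate stays at 50%.
- *Case B:* drained controls carry the full stent-arm risk. Control rate = 0.50 − f × (0.50 − stent rate). At a true 25% this is 48.75%, 47.5% and 45% for the three fractions, so the difference shrinks from 25 points to 23.75, 22.5 and 20.

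| f | Case A, true 25% | Case B, true 25% | Case A, true 30% | Case B, true 30% |
|---|---|---|---|---|
| 0 | 84.7% | 84.7% | 67.1% | 67.1% |
| 5% | 84.7% | 81.6% | 67.1% | 63.5% |
| 10% | 84.7% | 78.1% | 67.1% | 59.9% |
| 20% | 84.7% | 69.9% | 67.1% | 52.2% |

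The pooled normal approximation shows the same pattern for Case B at 25%: 83.4% falling to 80.0%, 76.3% and 67.8%.

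A third possibility is that failed drainage raises risk. If it adds 10 points for drained patients in both arms and f = 20% in each, the rates become 52% and 27%, and power at a true 25% is 83.7%.

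**The case against.** The strongest reply has three parts.

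First, this is a gap in wording rather than a flat contradiction. The phrase in Section 1.1 can be read as meaning the trial's own drainage step, and a site that read the whole protocol would be unlikely to treat a stented patient as a valid control. That is a fair account of what was probably intended. But sites enrol against the eligibility list, and as written the list does not carry that intention.

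Second, the bilirubin threshold, together with recruitment of patients who present with jaundice, should remove most patients with a working stent. This stands. A reader might infer from the gap that the control arm will be contaminated; the documents do not support that, because they say nothing about how many candidates arrive already drained. Nor is randomisation compromised: the same rule applies to both arms before allocation.

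Third, the power loss in Case B assumes that drained controls enjoy the full benefit of stenting. That is least plausible for the patients who can slip through, since their stent is recent or not working. This stands too. Case A shows no loss at all, so the 70% figure cannot be quoted alone as the expected consequence.

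An Eligibility Checklist is mentioned in Section 15 as a possible attachment but is not shown, so prior drainage may already be recorded somewhere.

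**Conclusion.** The concern holds as a mismatch between the eligibility rule and the control-arm definition. As written, Section 4.2 can admit patients for whom the control condition in Section 1.1 and the Summary is no longer available, and neither the described screening nor the planned analyses clearly identify them. This rests on the text and needs no power figure.

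The practical size is unknown. Under assumed fractions of 5%, 10% and 20% and a true stent-arm rate of 25%, power ranges from no loss (about 85%) down to about 82%, 78% and 70%. The lower end requires drained controls to carry the full stent-arm risk; the upper end requires them to keep the 50% control risk. The stronger conclusions, that contamination will occur or that the trial is materially underpowered for this reason, are not supported. The change is worth making because it is cheap and settles what the control arm means.

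**What to change.** Reconcile Section 4.2 with Section 1.1 and the Study Summary. The simplest route is to delete the words *for cholangitis* from the exclusion, so that any previous biliary drainage by ERCP or PTC excludes from randomisation, and to record prior drainage, yes or no, at screening.

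If the sponsor does intend to admit previously drained patients, the control-arm definition in Section 1.1 and the Summary should say so, and Section 7 should state how those patients are identified and reported in the analysis.

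The first route changes one eligibility line and adds one screening item. Its downside is the loss of a few otherwise eligible patients to accrual; the documents do not allow that number to be estimated.
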